**Aim 3: To refine the HINP program for future use.**

**A3a:** To explore HINP intervention arm participants' 1) satisfaction with the intervention, 2) recommendations for modifications on delivery modality, and 3) recommendations for intervention topics and content modifications.

**Study Design Overview:** The proposed study will take place in 3 phases and will involve a total of approximately 122 participants recruited from the Long-Term Follow-Up (LTFU) study cohort (See Section III below)-

- In Phase 1 we will develop a psychoeducational health insurance navigation program (HINP) through participant input and a series of advisory board meetings and individual interviews. We will also refine the program by recruiting a small group of LTFU study cohort members for an open pilot of the intervention.
- In Phase 2 we will pilot the feasibility, acceptability, and preliminary efficacy of the videoconferencing-based HINP with LTFU study cohort members.
- In Phase 3 we will further refine the program through study participant feedback.

Below we describe the activities for the three study phases. Detail on participant enrollment and consent procedures for all three phases is included in Section IV.

**Phase 1**

**Participant Focus Groups**

Four focus group interviews (approximately n=8 per group) will be conducted with randomly selected LTFU study participants (see Participant Focus Group Interview Guide); selection will be stratified according to Medicaid expansion status (Y/N), which we will determine based on participant demographic information from the LTFU data records. LTFU participants from the original and expansion cohort will be eligible and consented (Please refer to Sections III and IV for information on subject selection and consent procedures); we will assure inclusion of men and women. Groups will last about 60 minutes, and may be conducted through Zoom, a HIPAA compliant videoconferencing platform (see Maintaining Confidentiality in Section VII) or in-person. Participants will be provided \$50 remuneration by the University of Utah. Groups will be co-facilitated by co-investigators via a semi-structured interview guide (See Participant Focus Group Guide). The interviews will be recorded.

**Advisory Board Input on HINP**

Three advisory board meetings will be conducted, specifically, with national oncology clinicians and researchers and Boston-based experts. These groups will be co-facilitated by investigators via a semi-structured interview guide that contains the following domains: 1) barriers, 2) resources, 3) content, 4) intervention structure and

dose, 5) delivery and 6) selection criteria (See Advisory Interview Board Guide). Advisory board meetings will also be conducted through Zoom Videoconferencing, via phone, or in person. The advisory board focus groups will be recorded and used for quality improvement purposes of the HINP.

#### Expert Individual Interviews

We will conduct approximately 10 30-minute individual interviews with experts at the intersection of health insurance, navigation, cancer, and survivorship. Experts will include clinicians, oncology social workers, and health insurance specialists. Interviews will be recorded and used for tailoring and improvement of the HINP. Individual interviews will be facilitated by investigators using a semi-structured interview guide containing the same domains as the advisory board interviews. These interviews will also be conducted through Zoom Videoconferencing via phone, or in-person.

For both Advisory Board and Expert interviews, we will assent experts for participation in the interviews (See Advisory Board Interview Guide)

#### Qualitative Analyses to Inform HINP Development

For qualitative analyses of focus group, advisory board meetings, and individual interviews, all data will be analyzed by MGH and Utah study staff using NVivo qualitative software. Content analyses will be conducted including a structural thematic framework, categories, and coding plan. For focus group data, a coding framework will be developed for themes and codes according to participants' feedback on 1) barriers to accessing and using health insurance 2) resources to support health insurance access and use, 3) navigation program content, 4) intervention structure and dose, 5) program delivery, 6) program acceptability, 7) aspects of coverage that are not well understood (See Participant Interview Guide) For advisory board and individual interview feedback, a coding framework will be developed for themes and codes according to the domains of: 1) barriers, 2) resources, 3) content, 4) intervention structure and dose, 5) delivery and 6) selection criteria. To ensure coding reliability, coding discrepancies for participant focus groups will be resolved through discussion and comparison of raw data. Coding will continue until a high level of reliability (Kappa=  $\geq 0.80$ ) is established. Co-investigators will provide an expert review of the results. For expert and advisory board interviews, a Rapid Analysis method will be used.

#### Open Pilot with Participants

With feedback from the focus groups, advisory boards, and individual interviews, results will be interpreted, summarized, and finalized; the investigators will refine the HINP. Then, approximately 5-10 participants will be randomly selected to participate as pilot subjects (Please see Sections III and IV for information on subject selection and consenting procedures). Aspects of the study that will be piloted include the surveys, intervention, and exit interview. Participants will be remunerated \$20 for the completion of a baseline survey, a follow-up survey and the exit interview by the University of Utah. Final intervention and survey modifications will be made.

## **Phase 2**

### Pilot Trial Design

We will recruit and randomize approximately 80 LTFU participants to a health insurance navigation intervention or to enhanced usual care (Please see Sections III and IV for information on subject selection and consenting procedures). We have selected this sample size of approximately 40 per arm to enable evaluation of feasibility and acceptability goals as well as explore meaningful differences in the outcomes. Surveys will be conducted at baseline and 3-month post program completion follow-up via REDCap or mail. All participants will be asked to complete a follow-up survey approximately 3-months after the HINP intervention period (in other words approximately 5-months post pilot trial enrollment).). After completion of the follow-up survey, HINP participants will be contacted for an exit interview (see Phase 3 below). Participants will be remunerated \$20 for each survey and the exit interview by the University of Utah

### Study Arms

#### Enhanced Usual Care

Enhanced usual care will consist of a mailed or online copy of a health insurance resource guide.

#### Navigation Intervention

The intervention will be delivered via synchronous videoconferencing (real-time delivery and communication between the navigator and the participant) by a trained patient navigator (See Intervention Fidelity in Section VI) and will consist of 4, 30-minute sessions delivered every week, over the span of one month (for intervention development purposes, the pilot sessions will occur every week, over the course of one month). The navigation intervention group will also receive a mailed copy of the brochure.

#### Proposed Navigation Intervention Structure and Content

The program will be delivered via videoconferencing by a navigator over a 1-month period. Accordingly, patient navigation is delivered until the desired endpoint is achieved; we propose that this will be accomplished with 4 navigation sessions (See Table 1: Proposed HINP Intervention). The proposed program content was informed by: 1) aforementioned research identifying childhood survivors' difficulties with accessing and utilizing one's coverage and managing costs, 2) CCSS health insurance survey, and 3) ACA provisions that are relevant to survivors (e.g., prevention services exempted from cost sharing, sources of available coverage and eligibility, benefits policies that have cost-related implications like OOP costs, and essential health benefits such as prescription medications. Based on advisory board and individual interview feedback, the content and tailoring of information will be modified.

**Table 1: Proposed HINP Intervention**

**Session One: Learning About Survivorship Healthcare Needs**

**Sessions Two: Learning About Your Plan in Relation to Policy**

**Session Three: Navigating One's Own Plan**

## Session Four: Managing Care Costs

### Phase 3

#### Exit Interviews

For HINP participants after the follow-up survey, the study co-investigators will conduct in-depth interviews (see Participant Exit Interview Guide) via videoconferencing with the 40 intervention participants to assess survivors' 1) satisfaction with the intervention, 2) recommendations for modifications on overall session topics and intervention content (e.g., physician communication, cost management strategies), and 3) recommendations for modifications on delivery modality (e.g., number and length of sessions, videoconferencing delivery). These will last about 20 minutes and participants will be remunerated \$20 for their time by the University of Utah. The exit interviews will be recorded.

Exit interview data will be transcribed and analyzed using NVivo qualitative software. Content analyses will be conducted and co-investigators will provide an expert review.

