#### *Focus Group and Exit Interview Qualitative Data*

Once the focus groups are scheduled by [name] team, the data collection efforts will be led via MGH's Zoom program. The Phase 1 participant qualitative data will be collected and stored within MGH. Data will be collected by [name] team at Massachusetts General Hospital using recording devices. Audio recording files will be saved and uploaded into NVIVO software on Shared File Areas in the Partners network, which will only be accessible to IRB-approved study staff. NVIVO files will be sent securely via Partners Secure File Transfer or via SharePoint, which has been approved for use in this study. The Phase 3 qualitative data in the form of exit interviews will follow procedures detailed in Phase 1.

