### Phase 3 Assessments

After the completion of the follow-up survey, investigators will conduct In-depth exit interviews with the 40 intervention arm participants to assess participants' 1) satisfaction with the intervention, 2) recommendations for modifications on overall session topics and intervention content (e.g., physician communication, cost management strategies) and 3) recommendations for modifications on delivery modality (e.g., number and length of sessions, videoconferencing delivery) . Participants will be remunerated \$20 for their time by the University of Utah.

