### Data Monitoring Plan

Survey data will be collected via [name] team at the Huntsman Cancer Institute. Data will be collected via mailed/phone-based survey and through a secure web-based portal (REDCap). Data transmissions will be conducted between the CCSS coordinating

center and statistical center with [name] to generate the participant sample and to facilitate data access from the LTFU baseline and follow up surveys. While the majority of surveys will be done via web using REDCap, we will allow participants to complete the baseline and follow-up surveys through mail or phone to improve participation. To ensure security, participant data collected using paper and pencil records will be stored in a locked filing cabinet in a locked room at the Huntsman Cancer Institute at the University of Utah; electronic participant tracking databases will be stored on a secure server accessible only by IRB-approved members of [name] study staff. Data collected on paper and pencil forms or through phone-based surveys will be thoroughly cleaned and entered into the electronic REDCap database with a 10% check; discrepancies will be resolved by [name]. [name] will lead the pilot study data management and analyses, and transmit analytic data to MGH using the Hartwell Center's FTA protocol (located at <http://fta.stjude.org>), which is a web-based interface with a secure 128-bit encrypted web connection. Only study staff will have access to the study data on Shared File Areas. Data quality (including sessions participated in for the intervention group, data missingness, and recruitment rates) will be monitored monthly. Interim data analysis will be conducted throughout the trial and results will be reported in the annual ACS progress report.

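### The Phase 3 exit interviews ask whether video delivery should be modified, yet video is the sole mode stated for holding them

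*Combined protocol and SAP*

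**What the plan says.** Aim 3 (A3a, Section II) asks intervention participants three things: how satisfied they were, what they would change about the delivery modality, and what they would change about topics and content. The planned source is the exit interview. Under Phase 3, Exit Interviews, "the study co-investigators will conduct in-depth interviews (see Participant Exit Interview Guide) via videoconferencing with the 40 intervention participants". The same paragraph lists among the topics "recommendations for modifications on delivery modality (e.g., number and length of sessions, videoconferencing delivery", so video is one of the features on which participants are asked to comment.

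The interview is described again under Phase 3 Assessments in Section V: "investigators will conduct In-depth exit interviews with the 40 intervention arm participants to assess participants". That text repeats the topics and the payment but names no mode.

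**The concern.** A participant who found the video sessions unreliable, awkward or uncomfortable is asked to use the same channel again in order to say so. If such people decline more often than others, non-response to the interview is linked to the feature being assessed, and their reasons are under-represented in the feedback that is meant to shape the next version of the program.

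The step from survey to interview makes this concrete. Pilot Trial Design has participants contacted for the interview once the follow-up survey is done. Someone may return that survey by mail or phone and then be invited to an interview for which only video is named.

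At stake is one of the three qualitative questions of Aim 3, in a group of about 40 people.

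**Working it through.** **Step 1. Which modes are stated for which activity.**

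| Activity | Where | Mode stated |
|---|---|---|
| Participant focus groups | Phase 1, Participant Focus Groups | "may be conducted through Zoom, a HIPAA compliant videoconferencing platform"; the sentence goes on to allow in-person groups |
| Advisory boards | Advisory Board Input on HINP | Zoom, phone or in person |
| Expert interviews | Expert Individual Interviews | "These interviews will also be conducted through Zoom Videoconferencing via phone, or in-person" |
| Baseline and follow-up surveys | Section IX, Data Monitoring Plan | Mainly web, but "we will allow participants to complete the baseline and follow-up surveys through mail or phone to improve participation" |
| Exit interviews | Phase 3, Exit Interviews | Videoconferencing |
| Exit interviews | Phase 3 Assessments; Pilot Trial Design; University of Utah Site Roles; Section V table | None |
| Exit interviews | Focus Group and Exit Interview Qualitative Data | "The Phase 3 qualitative data in the form of exit interviews will follow procedures detailed in Phase 1"; for the focus groups, that section says "the data collection efforts will be led via MGH's Zoom program" |

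Every other activity in the table has an alternative to video or web. For the surveys the protocol gives its reason, which is participation. For the exit interviews one mode is named, and no section adds a second.

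**Step 2. Whether another planned source covers the same question.** The satisfaction items under Outcomes in Section VI ask about needs met, the kind of help received and helpfulness. None asks about delivery mode. Measures mentions open-ended questions but specifies none on mode. Sessions completed shows that someone stopped, not why. The count of people excluded for lack of an internet device concerns people who never enrolled.

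**Step 3. Illustration of size.** The documents give no uptake figure, so there is nothing to reproduce beyond the count of interviewees: 80 / 2 = 40. The rates below are assumptions.

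Let s be the share of the 40 who had trouble with video, a their interview uptake, and b the uptake of the others, taken as 0.9. Then

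share of interviewees who had trouble = s·a / (s·a + (1 − s)·b).

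For s = 0.25 and a = 0.5: 0.125 / (0.125 + 0.675) = 15.6%. In people, this is 5 of the 10 who had trouble and 27 of the other 30, so 5 / 32.

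| s (people of 40) | a = 0.9 | a = 0.7 | a = 0.5 | a = 0.3 |
|---|---|---|---|---|
| 10% (4) | 10% | 8.0% | 5.8% | 3.6% |
| 20% (8) | 20% | 16.3% | 12.2% | 7.7% |
| 25% (10) | 25% | 20.6% | 15.6% | – |
| 30% (12) | 30% | 25.0% | 19.2% | 12.5% |
| 35% (14) | 35% | 29.5% | 23.0% | – |

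(– = not calculated.)

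When a = b the formula returns s, so there is no distortion. When a < b the share falls below s.

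The expected number interviewed among those who had trouble is 40·s·a. It runs from 40 × 0.10 × 0.3 = 1.2 to 40 × 0.35 × 0.7 = 9.8 over the cells with a below 0.9.

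**The case against.** The strongest reply has five parts.

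- **The restriction is read from silence.** A reader might infer that the plan forbids any other mode. It does not. It names one mode and is silent on others, and its wording on mode is loose elsewhere. Maintaining Confidentiality lists phone among the channels of the MGH telehealth technology, and Potential Benefits calls the navigation sessions phone-delivered although Navigation Intervention has them by video. (Those last two passages need reconciling in their own right.) The exit interview guide, which is not part of the documents, may also address mode. This stands, and it is why the point is that video is the sole mode stated, not that other modes are barred.
- **The percentages measure something the plan does not estimate.** Exit interviews go to content analysis for themes, and no proportion is reported from them. On most of the assumed rates several people with video trouble would still be interviewed, so the theme would probably surface. This stands in large part. The table shows direction and possible scale, not bias in a planned estimate.
- **There is other evidence on the mode.** Sessions completed is a feasibility outcome and participation in sessions is monitored monthly. Device exclusions are counted. This stands in part: these sources show that a problem exists, but do not give the reasons of enrolled people who struggled.
- **The affected group is narrow.** Everyone enrolled has an internet device and consents to the interview at Phase 2 consent. All intervention participants are to be interviewed, and the interview is a single paid call of about 20 minutes. This reduces the likely effect but does not deal with connection quality or comfort.
- **Modality is wider than video.** The number and length of sessions fall under the same topic. That is true, but video is named beside them.

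**Conclusion.** The point holds as a modest, avoidable weakness in Aim 3. If the plan is followed as written, people who found video difficult may be less likely to be interviewed, and the feedback on modality could under-represent them. This rests on one assumption that the documents neither support nor contradict with data: that uptake of a video interview is lower among those people. The size is unknown.

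Two stronger conclusions are tempting and are not supported. A reader might infer that the modality findings will lean toward keeping video. The documents give no rates from which to show this, and with equal uptake the effect vanishes. A reader might also infer damage to the trial's comparison of arms. There is none: the interviews are held in the intervention arm only, come after the follow-up survey, and feed no randomized comparison or primary outcome. This is a cheap improvement, not a flaw that threatens the trial.

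**What to change.** In Phase 3, Exit Interviews, change the statement of mode to: *via videoconferencing or telephone, as the participant prefers*. Add the same statement to Phase 3 Assessments, which at present names no mode.

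Record the mode used for each interview. Report exit-interview uptake by number of sessions completed, so that selective participation can be seen. Do not compare recommendations between video and telephone interviewees: they chose their own mode, so mode is confounded with preference, and with at most 40 people the groups would be very small.

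The cost is one line in each of two sections and one extra data field. Interviewers, guide, length and payment stay as they are, and telephone contact with participants is already planned for recruitment, scheduling and surveys. The small downside is the loss of visual cues in the telephone interviews.

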### III. SUBJECT SELECTION

#### Participants: Inclusion and Exclusion Criteria

LTFU study staff at St. Jude Children's Research Hospital keep updated participant contact records for this study, which allows for participants to be approached for additional research studies. For Phases 1 and 2, the LTFU study staff will recruit a total of approximately 122 participants from the Long-Term Follow-Up Study cohort.

Phase 1 will involve recruitment of 32 participants for four focus groups and approximately 5-10 participants for the open pilot. Phase 1 participants will not be eligible for Phase 2 participation. For the focus group activities of this Phase, participants will be randomly selected stratified according to whether they reside in a state with or without Medicaid expansion, which LFTU staff will determine based on participant addresses available from the LTFU data records.

Phase 2 will involve recruitment of 80 randomly-selected participants for the pilot randomized trial. Participants will be randomly selected stratified according to whether they reside in a state with or without Medicaid expansion, which LFTU staff will determine based on participant addresses available from the LTFU data records.

Phase 3 participants will be recruited from the Intervention Arm of Phase 2 (approximately n=40).

For both Phases, we will exclude participants who : (1) do not have health insurance, (2) are under the age of 18, (3) are unable to give informed consent due to psychiatric or cognitive impairment as determined in consultation with study PI, patient navigator, or oncology social worker, and (4) do not have access to a smartphone, computer or tablet with internet access. Importantly, we will closely document and monitor the

numbers of individuals who are unable to participate given this final criterion, as it will further inform the feasibility of this intervention modality.

#### Sources of Subjects and Recruitment Methods

The Long-Term Follow-Up Study (LTFU) is an NIH-funded multi-institutional study of individuals who were diagnosed before 21 years of age with leukemia, CNS malignancies, Hodgkin's disease, non-Hodgkin's lymphoma, Wilm's tumor, neuroblastoma, soft tissue sarcoma, bone cancer or serious illness who survived at least five years after diagnosis. Eligible participants for the LTFU were identified through medical records and clinic lists at participating centers in the U.S., yielding a retrospectively ascertained cohort of adult childhood survivors with ongoing, longitudinal follow-up. The LTFU includes individuals diagnosed with cancer or serious illness between 1970-1999, recruited from over 25 pediatric oncology institutions in North America. Eligible participants for our study include 21,841 LTFU participants who are still alive and have available contact information.

